### 11.5.2. Study Population

Study Population
Age

 
GSK standard IDSL algorithms will be used for calculating age where birth date will be imputed as follows: 
 
Any subject with a missing day will have this imputed as day '15'.
 
Any subject with a missing date and month will have this imputed as '30th June'.
 
The year of the birth date will be captured in the pCRF
 
 
 
 
Age will then be derived as the integer value of [(DoB- date of Screening)/365.25]
 
 
Birth date will be presented in listings as 'YYYY'.
 

Body Mass Index (BMI)

 
Calculated as Weight (kg) / [Height (m) 2]
 

Treatment Compliance

 
Treatment compliance will be calculated based on the formula:  <math display="block">\text{Treatment Compliance} = \text{Number of Actual Doses} / (\text{Planned Treatment Duration in Days} * \text{Frequency})</math> 
 
Frequency is 2 for BID and 1 for QD. Treatment compliance could be greater than 100% if there are events of overdose. Cumulative compliance (since Day 1) at each visit will be calculated.
 
Planned Treatment Duration is defined as 1 day in period 1 and 1 day in period 2.
 

Extent of Exposure

 
Number of days of exposure to study drug will be calculated based on the formula:
 

Study Population
Duration of Exposure in Days = Treatment Stop Date – (Treatment Start Date) + 1

 
Participants who were randomized but did not report a treatment start date will be categorised as having zero days of exposure.
 
The cumulative dose will be based on the formula: Cumulative Dose = Sum of (Number of Days x Total Daily Dose)
 
If there are any treatment breaks during the study, exposure data will be adjusted accordingly.
 

11.5.3. Safety

ECG Parameters
RR Interval

 
IF RR interval (msec) is not provided directly, then RR can be derived as:           
 
[1] If QTcF is machine read, then:
 
 <math display="block">RR = \left[ \left( \frac{QT}{QTcF} \right)^3 \right] * 1000</math> 
 
If ECGs are manually read, the RR value preceding the measurement QT interval should be a collected value THEN do not derive.
 

Corrected QT Intervals

 
When not entered directly in the pCRF, corrected QT intervals by Fridericia's (QTcF) formulas will be calculated, in msec, depending on the availability of other measurements.
 
IF RR interval (msec) is provided then missing QTcF will be derived as:
 
 $QTcF = \frac{QT}{\sqrt[3]{\frac{RR}{1000}}}$

Laboratory Parameters

 
If a laboratory value which is expected to have a numeric value for summary purposes, has a non-detectable level reported in the database, where the numeric value is missing, but typically a character value starting with '<x' or '>x' (or indicated as less than x or greater than x in the comment field) is present, the number of significant digits in the observed values will be used to determine how much to add or subtract in order to impute the corresponding numeric value.           
 
Example 1: 2 Significant Digits = '< x' becomes x – 0.01
 
Example 2: 1 Significant Digit = '> x' becomes x + 0.1
 
Example 3: 0 Significant Digits = '< x' becomes x – 1
 
 
 
 
This imputation should be performed on the raw data before the conversion of units in CDISC studies to ensure correct imputation of missing data.

## 11.6. Appendix 6: Reporting Standards for Missing Data

### 11.6.1. Premature Withdrawals

Element	Reporting Detail
General	
 
Subject study completion (i.e. as specified in the protocol) was defined as one who has completed all phases of the study including the last visit.
 
If participants prematurely discontinue the study, additional replacement participants may be enrolled at the discretion of the sponsor and in consultation with the investigator
 
All available data from subjects who were withdrawn from the study will be listed and all available planned data will be included in summary tables and figures, unless otherwise specified.
 

Liver Chemistry Stopping Criteria	
 
Study treatment will be stopped for a subject if the following liver chemistry stopping criteria is met: 
 
ALT <math>\geq 3 \times</math> ULN; or
 
ALT <math>\geq 3 \times</math> ULN and total bilirubin <math>\geq 2 \times</math> ULN (<math>> 35\%</math> direct bilirubin); or
 
ALT <math>\geq 3 \times</math> ULN and INR <math>> 1.5</math> (INR is not a Protocol requirement)
 
 
 
 
Note: Refer to Appendix 4 of Protocol for details of the required assessments if a subject meets the above criteria.

QTc Stopping Criteria	
 
A subject who meets either bulleted criterion below will be withdrawn from the study: 
 
QTcF <math>> 500</math> msec
 
Change from baseline: QTcF <math>> 60</math> msec
 
 
 

### 11.6.2. Handling of Missing Data

Element	Reporting Detail
General	
 
Missing data occurs when any requested data is not provided, leading to blank fields on the collection instrument: 
 
These data will be indicated by the use of a “blank” in subject listing displays. Unless all data for a specific visit are missing in which case the data is excluded from the table.
 
Answers such as “Not applicable” and “Not evaluable” are not considered to be missing data and should be displayed as such.
 
 
 

Outliers	
 
Any participants excluded from the summaries and/or statistical analyses will be documented along with the reason for exclusion in the clinical study report.
 

#### 11.6.2.1. Handling of Missing and Partial Dates

Element	Reporting Detail
General	
 
Partial dates will be displayed as captured in subject listing displays.
 

Adverse Events	
 
The pCRF allows for the possibility of partial dates (i.e., only month and/or year) to be recorded for AE start and end dates; that is, the day or the month of the date may be missing.
 
Any fully or partially missing dates for adverse events will be raised to data management for resolution before DBR.
 

Element	Reporting Detail
	
 
If fully or partially missing dates are available following DBF, the following conventions will be applied for calculating the time to onset and the duration of the event:
 
 
Partially Missing Dates:
 
 
Missing Start Day: First of the month will be used unless this is before the start date of study treatment; in this case the latest study treatment start date will be used and hence the event is considered On-treatment as per Appendix 3 Study Phases and Treatment Emergent Adverse Events.
 
Missing Start Month: January will be used unless this is before the start date of study treatment; in this case the month of the latest study treatment start date will be used and hence the event is considered On-treatment as per Appendix 3 Study Phases and Treatment Emergent Adverse Events.
 
Missing Start Year: Current year will be used unless this is before the start date of study treatment; in this case the year of the latest study treatment start date will be used and hence the event is considered On-treatment as per Appendix 3 Study Phases and Treatment Emergent Adverse Events.
 
Missing Stop Day: Last day of the month will be used, unless this is after the stop date of study treatment; in this case the latest study treatment stop date will be used.
 
Missing Stop Month: December will be used, unless this is after the stop date of study treatment; in this case the latest month of study treatment stop date will be used.
 
Missing Stop Year: Current year will be used, unless this is after the stop date of study treatment; in this case the latest year of study treatment stop date will be used.
 
 
Fully Missing Dates:
 
Completely missing start or end dates will remain missing, with no imputation applied. Consequently, time to onset and duration of such events will be missing.

Concomitant Medications/ Medical History	
 
Partial dates for any concomitant medications recorded in the CRF will be imputed using the following convention: 
 
If the partial date is a start date, a '01' will be used for the day and 'Jan' will be used for the month
 
If the partial date is a stop date, a '28/29/30/31' will be used for the day (dependent on the month and year) and 'Dec' will be used for the month.
 
 
 
The recorded partial date will be displayed in listings.
 

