7.3. Method of Treatment Assignment

This is an open-label study and all the participants will be assigned to each of the following treatments in a non-randomized manner. All participants will receive Treatment 1 (IV infusion [concomitant with an inhaled dose]) first, and Treatment 2 (oral dose) second.

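### The SAP's rule for partial AE stop dates puts the end of some oral-period events before their start, and its start-date rule should say which period's dose it means

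*SAP*

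**What the plan says.** SAP section 11.6.2.1 sets conventions for AE dates that are still partial after database freeze. Their stated purpose is that "the following conventions will be applied for calculating the time to onset and the duration of the event".

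- **Stop day missing:** "Last day of the month will be used, unless this is after the stop date of study treatment"; if it is after, the most recent treatment stop date replaces it.
- **Stop month missing:** the same cap, in months: "December will be used, unless this is after the stop date of study treatment; in this case the latest month of study treatment stop date" is used.
- **Start day missing:** the first of the month is used unless it precedes the start of treatment; "in this case the latest study treatment start date will be used", and the event is then called on-treatment with reference to Appendix 3.

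The section does not require the stop to be on or after the start, does not keep the imputed date in the recorded month, and does not say which period's dates apply.

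Three design facts bear on this. SAP section 11.5.2 states: "Planned Treatment Duration is defined as 1 day in period 1 and 1 day in period 2". Protocol section 7.3 fixes the order: "All participants will receive Treatment 1 (IV infusion [concomitant with an inhaled dose]) first, and Treatment 2 (oral dose) second". Protocol sections 9.2.1 and 5.1.3 have AEs collected until the follow-up visit, which falls 7–14 days after the last dose.

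**The concern.** The convention suits continuous dosing, where most events fall between the first and last dose. Here treatment stops on the day it starts, so most of the AE observation window lies after the cap. For a participant who receives both doses, the most recent start and stop dates are both the oral dosing day.

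Two things could go wrong. An imputed stop can precede a known start, which gives a meaningless duration. And an event that followed the inhaled and IV doses could be dated to the oral dose. With six participants, one event placed under the wrong treatment changes a by-treatment incidence by 1/6, about 17 percentage points.

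**Working it through.** The documents give no figure to reproduce. The check applies the written missing-day rules to dates.

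**Notation.** D1 is the Period 1 dosing day and D2 the oral dosing day. D2 is at least D1 + 14 days (the washout). S is the AE start and T its true stop.

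**1. Stop rule, oral period.** Suppose S is after D2. The end of the month containing T is on or after T, T is on or after S, and S is after D2. The month end is therefore always after D2, the cap always applies, and the imputed stop is D2, which is before S. The result does not depend on the calendar.

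*Example (assumed dates: D1 = 5 March, D2 = 19 March).* An AE starts on 22 March and only the month March is recorded for its stop. 31 March is after 19 March, so the stop becomes 19 March, and 19 − 22 = −3 days. The SAP gives no formula for AE duration. If 1 day is added, as in its exposure formula, the result is −2.

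**2. Stop rule, Period 1.**
- *Literal reading (cap at D2).* S is before D2, and the imputed stop is either D2 or a month end no earlier than T, so the stop never precedes the start.
- *Per-period reading (cap at D1).* Step 1 applies with D1 in place of D2, so every Period 1 AE that begins after the dosing day is inverted.

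**3. Start rule, Period 1.** If the AE falls in the month of D1, and D1 is not the 1st, the first of that month precedes D1.
- *Literal reading.* The start becomes D2. With the dates above, an AE that truly began on 7 March, with only March recorded, is set to 19 March. With doses on 20 March and 3 April, an AE recorded as March is set to 3 April, outside its recorded month.
- *Per-period reading.* The first example becomes 5 March and stays in Period 1.

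Under the literal reading, a moved event with a complete stop date in Period 1 also ends before it starts.

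**4. Enumeration.** The assumptions were all 365 Period 1 dosing dates in a calendar year; washouts of 14, 21 and 28 days; Period 1 onsets from D1 to the day before D2; oral-period onsets 1–14 days after D2; and durations of 0–7 days.

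| Case | 14 days | 21 days | 28 days |
|---|---|---|---|
| Oral-period AE, stop day missing: stop before start (365 × 14 × 8 cases) | 40,880/40,880 | 40,880/40,880 | 40,880/40,880 |
| Period 1 AE, stop day missing, literal: stop before start | 0/40,880 | 0/61,320 | 0/81,760 |
| Period 1 AE starting after D1, stop day missing, per period: stop before start | 37,960/37,960 | 58,400/58,400 | 78,840/78,840 |
| Period 1 AE, start day missing, literal: moved to oral day | 3,850/5,110 (75%) | 4,893/7,665 (64%) | 5,348/10,220 (52%) |

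In the first row, 36% of the imputed stop dates also leave the recorded month. The moved cases in the last row are exactly those described in step 3. These are shares of date combinations, not forecasts of how often the error would occur.

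**5. After a change.** Setting the stop to the later of S and the earlier of month end and D2 + 14 days gave 0 of 40,880 inversions in the oral period.

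The missing-month and missing-year rules have the same structure but were not enumerated.

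**The case against.** **The start rule can be read per period.** Section 11.6.2.1 points to Appendix 3, which classifies events relative to the treatment within each period and uses period dates for the treatment-emergent flag. This stands: the move to the oral period is an ambiguity, not a demonstrated misallocation. It does not rescue the stop rule, because the per-period reading spreads the inversion to Period 1. Neither reading removes both problems.

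**Counts are mostly safe.** The conventions serve time to onset and duration, the AE endpoint is incidence, and none of safety tables 3.1–3.4 is titled as summarising duration or time to onset. This stands for the stop rule, which changes no AE count. The start rule could change by-treatment counts under the literal reading, because the imputed date feeds the on-treatment classification.

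**The trigger is rare and visible.** Partial AE dates are queried before database release and shown as captured in listings, all AEs are listed, and participants are resident to at least Day 8 in each period. Completely missing dates are not imputed. All of this stands. Participants are at home between Day 8 of Period 1 and the oral period, however, so incompletely recalled dates from that interval are plausible.

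**Stronger readings.** A reader might infer that nearly every partial date is imputed wrongly. The documents do not support this: the literal stop rule inverts no Period 1 event that has a complete start date, and the literal start rule moves 52–75% of the enumerated Period 1 cases, not all. A reader might also infer that the error would go unnoticed for want of a comparator. A comparator would not reveal a date error, whereas the queries and listings could.

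**Conclusion.** The stop rule is wrong for this design. Any AE that starts after the oral dosing day and has a missing stop day is given a stop before its start. That follows from the one-day treatment periods and does not depend on the assumed dates.

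The start rule is ambiguous. Read literally, it sets a Period 1 AE known only by month to the oral dosing day when that month contains a Period 1 dose not given on the 1st. A per-period reading avoids this, and the SAP should state it.

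The point is minor. It reaches only AE dates still partial after freeze, and the documents do not indicate how many there will be. It affects AE duration and time to onset and, under the literal reading only, by-treatment AE counts. The conclusion assumes a participant who receives both doses. For one who receives only the Period 1 treatment, the most recent stop date is the Period 1 dosing day, and the inversion applies there under either reading.

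**What to change.** In SAP section 11.6.2.1:

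1. Impute a partial AE stop date as the earlier of the end of the recorded month and the participant's last study contact, and never before the AE start date.
2. Where the first of the recorded month falls before the dose, use the dosing date of the period to which the event belongs, in place of the most recent treatment start. Take the period from the AE record. The documents do not show whether the AE page captures it; if it does not, infer it from the recorded month, the AE stop date and the visit at which the event was reported.
3. Apply the same principles to the missing-month and missing-year rules.

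Using the Period 1 dosing date as the earliest imputed start fits Protocol section 9.2.1, which sends occurrences before treatment to medical history instead of the AE page.

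The cost is a few sentences in the SAP and the matching programming. No data collection, dosing or clinical procedure changes.

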## 11.7. Appendix 7: Values of Potential Clinical Importance

### 11.7.1. Laboratory Values

Haematology				
Laboratory Parameter	Units	Category	Clinical Concern Range	
			Low Flag (< x)	High Flag (>x)
Haematocrit	Ratio of 1	Male		0.54
		Δ from BL	↓0.075	
Haemoglobin	g/L	Male		180
		Δ from BL	↓25	
Lymphocytes	x10  / L		0.8	
Neutrophil Count	x10  / L		1.5	
Platelet Count	x10  / L		100	550
White Blood Cell Count (WBC)	x10  / L		3	20

Clinical Chemistry				
Laboratory Parameter	Units	Category	Clinical Concern Range	
			Low Flag (< x)	High Flag (>x)
Albumin	mmol/L		30	
Calcium	mmol/L		2	2.75
Creatinine	mmol/L			1.3 x ULN
Creatinine	mmol/L	Δ from BL		↑ 44.2
Glucose	mmol/L		3	9
Phosphorus	mmol/L		0.8	1.6
Potassium	mmol/L		3	5.5
Sodium	mmol/L		130	150

Liver Function				
Test Analyte	Units	Category	Clinical Concern Range	
ALT/SGPT	U/L	High	≥ 2x ULN	
AST/SGOT	U/L	High	≥ 2x ULN	
AlkPhos	U/L	High	≥ 2x ULN	
T Bilirubin	μmol/L	High	≥ 1.5xULN	
T. Bilirubin + ALT	μmol/L U/L	High	1.5xULN T. Bilirubin + ≥ 2x ULN ALT	

### 11.7.2. ECG

ECG Parameter	Units	Clinical Concern Range	
		Lower	Upper
Absolute			
Absolute QTc Interval	msec		≤ 450
Absolute PR Interval	msec	< 120	< 220
Absolute QRS Interval	msec		≤ 120
Absolute Ventricular rate	beats/min	<35	>100
Change from Baseline			
Increase from Baseline QTc	msec		> 60

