### 11.7.3. Vital Signs

Vital Sign Parameter (Absolute)	Units	Clinical Concern Range	
		Lower	Upper
Systolic Blood Pressure	mmHg	≥ 90	≤ 140
Diastolic Blood Pressure	mmHg	≥ 40	≤ 90
Heart Rate	bpm	≥ 40	≤ 90
Respiration rate	breaths/min	≥ 8	≤ 20
Oral Temperature	°C	≥ 35.5	≤ 37.8

Vital Sign Parameter (Change from Baseline)	Units	Clinical Concern Range	
		Decrease	Increase
Systolic Blood Pressure	mmHg	≥ 40	≥ 40
Diastolic Blood Pressure	mmHg	≥ 20	≥ 20
Heart Rate	bpm	≥ 30	≥ 30

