**CONFIDENTIAL**

206764

ICH: Listings					
No.	Population	IDSL / Example Shell	Title	Programming Notes	Deliverable
All Laboratory					
21.	Safety	LB6	Listing of All Laboratory Data for Participants with Any Value of Potential Clinical Importance	ICH E3	SAC
22.	Safety	LB6	Listing of Laboratory Values of Potential Clinical Importance		SAC
23.	Safety	LB14	Listing of Laboratory Data with Character Results	ICH E3	SAC
24.	Safety	UR2B	Listing of Urinalysis Data for Participants with Any Value of Potential Clinical Importance	ICH E3	SAC
ECG					
25.	Safety	CP_EG4	Listing of All ECG Values for Participants with Any Value of Potential Clinical Importance	IDSL	SAC
26.	Safety	CP_EG4	Listing of ECG Values of Potential Clinical Importance	IDSL	SAC
27.	Safety	CP_EG6	Listing of All ECG Findings for Participants with an Abnormal ECG Finding	IDSL	SAC
28.	Safety	CP_EG6	Listing of Abnormal ECG Findings	IDSL	SAC
Vital Signs					
29.	Safety	VS5	Listing of All Vital Signs Data for Participants with Any Value of Potential Clinical Importance	IDSL	SAC
30.	Safety	VS5	Listing of Vital Signs of Potential Clinical Importance	IDSL	SAC

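### SAP 11.7.2 and 11.7.3 mix acceptable limits with values of concern, so 13 of 16 absolute ECG and vital-sign criteria, applied as printed, flag the wrong side.

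*SAP*

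**What the plan says.** SAP Appendix 7 (section 11.7) defines values of potential clinical importance. Its ECG and vital-sign tables share the column heading "Clinical Concern Range", split into Lower and Upper for absolute values.

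- **ECG (11.7.2).** "Absolute QTc Interval": upper ≤ 450 msec. "Absolute PR Interval": lower < 120, upper < 220. "Absolute QRS Interval": upper ≤ 120. "Absolute Ventricular rate": lower < 35, upper > 100. "Increase from Baseline QTc": > 60 msec.
- **Vital signs (11.7.3), absolute.** "Systolic Blood Pressure": ≥ 90 and ≤ 140. Diastolic pressure: ≥ 40 and ≤ 90. Heart rate: ≥ 40 and ≤ 90. Respiration: ≥ 8 and ≤ 20. Temperature: ≥ 35.5 and ≤ 37.8.
- **Vital signs, change from baseline.** A decrease or increase of ≥ 40 (systolic), ≥ 20 (diastolic) or ≥ 30 (heart rate).
- **Laboratory (11.7.1).** Haematology and chemistry flag low values below a limit and high values above one. Liver tests flag values at or above a multiple of the upper limit of normal.

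SAP 11.9.8 plans four listings that select on these ECG and vital-sign limits: Listings 25 and 26 for ECG (26 is the "Listing of ECG Values of Potential Clinical Importance") and Listings 29 and 30 for vital signs. Their programming notes cite only the sponsor's display standards. Nothing says that any operator should be reversed.

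**The concern.** Under a heading that announces values of concern, an entry should describe the value that triggers a flag. Some entries do, and others describe the value that should not. The PR row does both: its lower entry (< 120) is a concern condition and its upper entry (< 220) is an acceptable limit.

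No single reading rescues the ECG table. If every entry is a concern condition, QTc, PR upper and QRS are backwards. If every entry is an acceptable limit, PR lower, ventricular rate and QTc change are backwards.

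At stake is the content of four safety listings. ECG and vital-sign parameters are part of a secondary endpoint (Protocol section 4; SAP 2.2). With six participants, the individual listings carry much of the information, since Tables 3.10 and 3.11 summarise change from baseline.

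**Working it through.** The SAP gives no figure to reproduce, so the check classifies each entry by direction and then applies the entries as literal flag rules to illustrative values.

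**Step 1: classify.** For absolute values, Lower with < or Upper with > is a concern condition. Lower with ≥, or Upper with ≤ or <, is an acceptable limit. A change from baseline given as > or ≥ is a concern condition.

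| Group | Acceptable limit | Concern condition | Total |
|---|---|---|---|
| ECG, absolute | 3 (QTc; PR upper; QRS) | 3 (PR lower; ventricular rate lower and upper) | 6 |
| Vital signs, absolute | 10 | 0 | 10 |
| ECG, change | 0 | 1 | 1 |
| Vital signs, change | 0 | 6 | 6 |
| All | 13 | 10 | 23 |

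Absolute entries: 3 + 10 = 13 of 6 + 10 = 16, or 81%. All entries: 13 of 23, or 57%. ECG table alone: 3 of 7.

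**Step 2: confirm the intended side.** Protocol section 6.2 excludes a mean QTcF above 450 msec, a blood pressure persistently above 140/90 mmHg and a mean heart rate outside 40–90 bpm. These match SAP cut-offs, with the abnormal side opposite to the printed operators. The comparison for QTc assumes that the SAP entry refers to QTcF.

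**Step 3: apply the absolute entries literally.**

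| Parameter | Flagged as printed | Not flagged as printed |
|---|---|---|
| QTc (msec) | 400, 450 | 451, 480, 501 |
| PR (msec) | 110, 160, 219 | 220, 240 |
| QRS (msec) | 90, 120 | 130 |
| Systolic BP, Lower and Upper as separate flags | 80, 120, 160 | none |
| Systolic BP, Lower and Upper required together | 120 | 80, 160 |

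The other vital signs have the same form. As separate flags they catch every possible value; taken jointly they catch only normal ones.

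**Step 4: does the change rule close the QTc gap?** It flags a rise above 60 msec.

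- 430 to 480: 480 − 430 = 50, not flagged.
- 445 to 501: 501 − 445 = 56, not flagged.
- 390 to 455: 455 − 390 = 65, flagged.
- 440 to 510: 510 − 440 = 70, flagged.

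A QTc above 450 is therefore caught only when the rise also exceeds 60.

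**Step 5: reverse the QTc operator and keep the cut-off.** With > 450, the values 451, 480 and 501 are flagged, and 400 and 450 are not. That is the opposite of the printed rule.

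**The case against.** The strongest case on the other side is that this is a drafting slip that would not survive first use. Literal separate flags would mark every vital-sign reading, which is hard to miss in six participants. The Protocol's exclusion criteria show the abnormal side for QTcF, blood pressure and heart rate. The listings are descriptive, and no hypothesis is tested (SAP 2.4). This stands as a reason to expect discovery. But the correction would then rest on an undocumented programming judgement, and the Protocol's exclusion criteria give no cut-off for PR, QRS, respiration or temperature.

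Four stronger readings are tempting, and the documents do not support them.

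- A reader might infer that a QTc above 450 would vanish from the report. Listing 25 prints all ECG values for any participant with one flagged value. On the literal reading any PR below 220 is a flag, so a QTc of 480 would very probably be printed there, though not as a flagged value. Whether Listing 26 would also show it depends on whether its shell selects single parameters or whole ECG records, and the documents do not include the shell.
- A reader might infer that these four listings are the only place abnormal results appear. Table 3.9 and Listings 27 and 28 cover ECG findings, and abnormalities judged clinically significant are adverse events (Protocol Appendix 5) that reach Listing 13. The four listings are the only displays selected by these numeric cut-offs.
- A reader might infer that participant protection is weakened. The QTcF withdrawal criteria (above 500 msec, or a change above 60 msec) are stated separately and in the right direction in Protocol 8.1.2 and SAP 11.6.1.
- A reader might infer that the ECG table is wholly inverted. Three of its six absolute entries are correctly directed, as is its change entry.

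**Conclusion.** The point holds as an error in a stated reporting rule. Thirteen of 16 absolute entries contradict their own column heading, and following them as printed puts wrong content in Listings 25, 26, 29 and 30: normal readings flagged, and QTc above 450 msec not flagged unless it has also risen by more than 60 msec.

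The effect is confined to descriptive safety listings. No primary endpoint, pharmacokinetic parameter or withdrawal rule uses these tables.

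The conclusion rests on two assumptions: that the heading means what it says, which the correctly directed entries and the laboratory tables support, and that no display specification outside these documents reverses the operators. The cut-off values themselves are not in question. The point should be settled before the listings are programmed.

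**What to change.** In SAP 11.7.2 and 11.7.3, restate every absolute entry as an out-of-range flag at the existing cut-offs, and say that Lower and Upper are separate conditions joined by 'or':

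- QTc > 450 msec
- PR < 120 or ≥ 220 msec
- QRS > 120 msec
- Systolic BP < 90 or > 140 mmHg
- Diastolic BP < 40 or > 90 mmHg
- Heart rate < 40 or > 90 bpm
- Respiration < 8 or > 20 breaths/min
- Temperature < 35.5 or > 37.8 °C

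For PR, ≥ 220 is the exact complement of the printed < 220. The sponsor should confirm whether a value of exactly 220 is to be flagged. Ventricular rate and all change-from-baseline entries stay as they are.

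The cost is an edit to two tables. It needs no new data or analysis and changes nothing in clinical management.
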